6.5.4 Survival

The primary estimate of the effect of treatment on survival as an efficacy endpoint will include both death and death equivalent as components, will pool participants randomized to 30 mg/d CNM-Au8 and 60 mg/d CNM-Au8 in the FAS analysis set, and will include baseline age as an additional covariate in adjusted models. Otherwise, summaries and analyses of time to death or death equivalent are the same as specified in the M-SAP.

The estimand estimated by the logrank test is the deviation in expected survival times in the FAS population. The estimand is defined by the following attributes:

Treatment: CNM-Au8 administered orally at dosages of 30 mg/d and 60 mg/d vs. placebo.

Population: FAS population as defined in Section 6.1.

Variables: time to earlier of death or death equivalent.

Intercurrent event: treatment discontinuation: handled via treatment policy approach, all data will be used including data collected during the placebo-controlled period after treatment discontinuation. Missing data post-treatment will not be imputed, handled via missing completely at random assumption.

Population-level summary: difference in survival curves of active treatment and placebo.

In the presence of a significant difference by the logrank test, inference on whether active treatment extended survival will be based on the hazard ratio estimated from an unadjusted Cox proportional hazards regression.

Survival to the end of the placebo-controlled period will also be analyzed in the ECM, ERO, EPP, STF, SFN, and SRO analysis sets. Survival analyses that include follow-up beyond the placebo-controlled period will be analyzed in the ERO analysis set.

Listings of all participants in the FAS, ECM, ERO, EPP, STF, and SRO analysis sets will document whether each participant had died, had reached a death equivalent endpoint, or was alive and free of a death equivalent and the study day of death, death equivalent, or last known alive and free of a death equivalent for each analysis timepoint.

6.5.5 Random-slopes Model

The specification of the random-slopes linear mixed model and the primary linear contrast for estimating differences in mean rate of progression in a given continuous efficacy endpoint (ALSFRS-R total and domain scores, HHD upper extremity, lower extremity, and global average percentages, SVC, FVC by home spirometry, quantitative voice characteristics, serum creatinine, serum NfL, urinary p75[ECD], ALSAQ-40 domain scores and SI, and CNS-BFS total score) are revised from those specified in the M-SAP to include a main effect of treatment and with the modification that treatment group is a three-level variable (i.e., placebo, 30 mg/d CNM-Au8, and 60 mg/d CNM-Au8).

The model will include fixed terms for month since the Baseline Visit, treatment group, treatment group \times month interaction, centered years since ALS symptom onset and centered years since ALS symptom onset \times month interaction, centered delta-FRS and centered delta-FRS \times month interaction, centered baseline riluzole use and centered baseline riluzole use \times month interaction, and centered baseline edaravone use and centered baseline edaravone use \times month interaction. The following equations describe the model with regimen random effects:

$$\begin{aligned}
 Y_{ij} &= \gamma_1 + a_{k(i)}^0 + b_i^0 + \gamma_2 t_i + \boldsymbol{\gamma}'_3 \mathbf{z}_i \\
 &+ (\gamma_4 + a_{k(i)}^1 + b_i^1 + \gamma_5 t_i + \boldsymbol{\gamma}'_6 \mathbf{z}_i) m_{ij} + \epsilon_{ij} \\
 \{a_k^0, a_k^1\} &\sim N(\mathbf{0}, \boldsymbol{\Sigma}_r), \{b_k^0, b_k^1\} \sim N(\mathbf{0}, \boldsymbol{\Sigma}_p), \epsilon_{ij} \sim N(0, \sigma_\epsilon^2) \\
 \text{Cov}(\mathbf{a}_k, \mathbf{b}_k) &= \mathbf{0}, \text{Cov}(\mathbf{a}_k, \boldsymbol{\epsilon}_{i\cdot}) = \mathbf{0}, \text{and } \text{Cov}(\mathbf{b}_k, \boldsymbol{\epsilon}_{i\cdot}) = \mathbf{0}
 \end{aligned} \tag{eqn. 2}$$

where Y_{ij} is a given efficacy endpoint measured in participant i at visit j , $a_{k(i)}^0$ and $a_{k(i)}^1$ are random intercept and slope for regimen k to which participant i was assigned, b_i^0 and b_i^1 are random intercept and slope for participant i , \mathbf{z}_i is the vector of covariates (centered time since onset, centered delta-FRS, centered baseline riluzole use, and centered baseline edaravone use) for participant i , m_{ij} is the time from baseline to observation j for participant i in months calculated as days \times 12 / 365.25, t_i is an indicator variable for treatment t to which participant i was assigned, $\gamma_1, \gamma_2, \gamma_3, \gamma_4, \gamma_5$, and $\boldsymbol{\gamma}_6$ are estimated parameters and vectors of parameters for the fixed effects, and ϵ_{ij} is the residual for observation j for participant i . The regimen-specific random effects are normally distributed with mean $\mathbf{0}$ and unstructured covariance matrix $\boldsymbol{\Sigma}_r$. The participant-specific random effects are normally distributed with mean $\mathbf{0}$ and unstructured covariance matrix $\boldsymbol{\Sigma}_p$. The residuals for a given participant are normally distributed with mean 0 and variance σ_ϵ^2 . The regimen-specific random effects, participant-specific random effects, and residuals are uncorrelated.

The following SAS code specifies the model:

```

proc mixed data=xxx method=reml;
  class regimen id trtrnd;
  model Value = trtrnd|month
            sx2b1|month dFRS|month rlz|month edv|month / solution cl;
  random intercept month / subject=regimen type=un;

```

```
random intercept month / subject=id type=un;
```

where month is time in months from the Baseline Visit (assuming 12 months in an average of 365.25 days per year) and other fields are the same as identified above in Section 6.5.3. The primary estimand will be the treatment-dependent difference in slopes. The estimate and its 95% Wald confidence bounds will be obtained by a linear contrast of adjusted means.

The estimand estimated by the primary linear contrast of the random-slopes linear mixed model is the difference in mean rate of progression of a given continuous efficacy endpoint in the two active treatment groups relative to the placebo group in the FAS population. The estimand is defined by the following attributes:

Treatment: CNM-Au8 administered orally at dosages of 30 mg/d and 60 mg/d vs. placebo.

Population: FAS population as defined in Section 6.1.

Variables: mean rate of change in endpoint from baseline to the Week 24 Visit.

Intercurrent event: treatment discontinuation: handled via treatment policy approach, all data will be used including data collected during the placebo-controlled period after treatment discontinuation. Missing data post-treatment will not be imputed, handled via missing at random assumption.

Population-level summary: difference in conditional mean slopes of active treatment relative to placebo.

Inference from these analyses is supportive of inference from the Bayesian shared-parameter, repeated-measures model for the primary endpoint and inference from the repeated-measures linear mixed model for secondary endpoints.

The following SAS code specifies the linear contrast assuming that the sort order for treatment group is placebo, 30 mg/d CNM-Au8, and 60 mg/d CNM-Au8:

```
estimate "3|Act vs Plb|Slope (/mn)"  
        month 0 trtrnd*month -2 1 1 / cl divisor=2;
```

A significant difference in slopes in the direction of improved function would support inference that the treatment reduced rate of progression for the efficacy endpoint being tested.

A separate supportive analysis for clinical endpoints (ALSFERS-R total and domain scores, HHD upper extremity, lower extremity, and global average percentages, SVC, FVC by home spirometry, quantitative voice characteristics, ALSAQ-40 domain scores and SI, and CNS-BFS total score) will include centered baseline serum NfL level and the interaction of centered baseline serum NfL level and study month as additional covariates.

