This clinical protocol will test CNM-Au8 at doses of 30 mg and 60 mg versus placebo in a randomized, double-blind manner, to determine if CNM-Au8 can demonstrate sufficient efficacy and safety on accepted clinical and preclinical outcomes for the treatment of ALS. The investigation of two doses of the study drug is based on counsel from the FDA recommending including a dose finding strategy in the study. The 30 mg and 60 mg doses of CNM-Au8 selected for the study achieve at least comparable AUC exposure in humans as those shown to demonstrate neuroprotection efficacy in nonclinical animal studies, and demonstrated minimal treatment emergent adverse events in the Phase 1 First-In-Human study in healthy volunteers.

Allocation to Treatment Regimens

Participants must first be screened under the Master Protocol before they are randomized to an RSA.

As soon as pre-defined criteria for futility for the RSA are met, or the target number of randomized participants has been reached, enrollment will stop in the RSA.

Number of Planned Participants and Treatment Groups

The number of planned participants for this regimen is approximately 160.

There are 2 treatment groups for this regimen, active and placebo. Participants will be randomized in a 3:1 ratio to active treatment or placebo (i.e., 120 active: 40 placebo). Half of the active treatment group will receive CNM-Au8 30mg/day and the other half will receive 60mg/day (i.e., 60 at 30mg/day: 60 at 60mg/day).

Planned Number of Sites

Research participants will be enrolled from approximately 60 centers in the US.

Treatment Duration

The maximum duration of the placebo-controlled treatment portion is 24 weeks.

Follow-up Duration

At the conclusion of the 24-week placebo-controlled Treatment Period of the study, all participants will either schedule a 28-day follow up phone call and end their participation in the regimen or have the option to receive CNM-Au8 in the Open Label Extension (OLE) phase of the study.

In the OLE, CNM-Au8 will be provided by Clene Nanomedicine, until the primary results of the 24 week double-blind portion of the study are available, or Clene or sponsor terminate support or development of CNM-Au8 for ALS.

Total Planned Trial Duration

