- Efficacy Per-protocol (EPP) Set: The subset of participants in the FAS analysis set who initiated study treatment and who were not involved in protocol deviations that affected the scientific integrity of the trial as documented prior to data lock, classified according to the treatment they actually received. Inclusion or exclusion from the EPP analysis set of any participant for whom treatment assignment was unblinded prior to data lock will be governed by the prespecified criteria above. If a participant's data is truncated for inclusion in the EPP analysis set due to non-adherence to protocol-specified dosing, clinical events observed up to 28 days after the censoring event will be included in the EPP analysis set. For all other events leading to truncation of a participant's data, no events beyond that date will be included. Data from placebo participants shared from other regimens will not be truncated due to non-adherence to protocol-specified dosing.

Applicable analysis sets (FAS, ECM, EPP, STF, and STN) will include shared placebo participants from regimens A, B, and D. Data from shared placebo participants will include visits and events that occurred on or before the date of the final placebo-controlled period follow-up of an RGA, RGB, or RGC participant. As only concurrently enrolling regimens are contributing to efficacy analyses, the FAS and ECC analysis sets are synonymous and only the FAS analysis set will be referenced. As regimen A is administered by subcutaneous injection and regimens B and D are administered orally, only regimens B and D will contribute shared placebo participants for the ECM and STN analysis sets.

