6.5.12 Subgroup Analyses

In addition to the subgroups specified in the M-SAP, the following additional subgroups will be analyzed in the random-slope model (see Section 6.5.5) for primary and secondary efficacy endpoints in the FAS analysis set:

- Baseline use of riluzole and edaravone (neither, riluzole only, edaravone only, both),
- Age (less than 65 years vs. 65 years or older),
- Sex (female vs. male),
- Race (white vs. any minority race with greater than 5% prevalence in the sample),
- Ethnicity (Hispanic or Latino vs. non-Hispanic or Latino),

- Weight (less than 43 kg, 43 to less than 56 kg, 56 to less than 77 kg, 77 to less than 150 kg, 150 kg or more),
- BMI (less than 18.5 kg/m², 18.5 to less than 25 kg/m², 25 to less than 30 kg/m², 30 to less than 40 kg/m², 40 kg/m² or more),
- Chronic kidney disease (CKD) stage (stage 1 or better [eGFR 90 mL/min/1.73m² or more], stage 2 [eGFR 60 to 89 mL/min/1.73m²], stage 3 [eGFR 30 to 59 mL/min/1.73m²], stage 4 [eGFR 15 to 29 mL/min/1.73m²], stage 5 [eGFR less than 15 mL/min/1.73m²]),
- Time since onset of weakness (less than 18 months vs. 18 months or longer),
- El Escorial and time since onset of weakness (El Escorial definite and less than 18 months vs. not both),
- Baseline symptom severity (all ALSFRS-R questions scored 2 or greater vs. any question scored 0 or 1),
- Early disease state (all ALSFRS-R questions scored 2 or greater, SVC 80%-predicted or greater, and time since symptom onset less than 24 months vs. not meeting all three criteria),
- Baseline serum urate concentration (less than 5.5 mg/dL vs. 5.5 mg/dL or greater),
- Baseline serum NfL concentration (by median split),
- Baseline delta-FRS score (less than 0.47 points/year, 0.47 to less than 1.11 points/year, 1.11 points/year or greater),
- Site of onset (any bulbar onset, no bulbar onset),
- Site (individual sites with at least 5 participants per treatment group and all participants from sites with fewer than 5 participants per treatment group pooled).

For each classification, unknown, not reported, and missing will be considered one group. All individuals not included in a specified subgroup will be combined into a mixed, "other" group. The "other" group will be included in analyses if its prevalence is greater than 5%; otherwise, the "other" group will be excluded.

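### The random-slopes intervals ignore the uncertainty in a regimen variance estimated from four regimens; if regimens differ moderately, nominal 95% coverage falls to about 90-92%

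*SAP*

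**What the plan says.** The random-slopes model in SAP 6.5.5 is fitted by REML ("proc mixed data=xxx method=reml") with a regimen-level term "random intercept month / subject=regimen type=un". That is three regimen covariance parameters: intercept variance, slope variance and their covariance. The MODEL statement asks only for the solution and confidence limits, with no degrees-of-freedom option. The text then states: "The estimate and its 95% Wald confidence bounds will be obtained by a linear contrast of adjusted means".

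SAP 6.1 fixes how many regimens inform those parameters. The full analysis set (FAS) "will include shared placebo participants from regimens A, B, and D", which with Regimen C makes four. In the common-mode-of-administration (ECM) set there are three, because "only regimens B and D will contribute shared placebo participants for the ECM and STN analysis sets".

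SAP 6.5.5 calls the analysis supportive of the Bayesian primary analysis and of the repeated-measures analyses of secondary endpoints. SAP 6.5.12 applies the same model to the added subgroups, which "will be analyzed in the random-slope model". Protocol 9.3 expects no systematic difference in the primary endpoint between controls of different regimens.

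**The concern.** Active drug is given only in Regimen C. The 40 randomized placebo participants in C share C's regimen slope with the active arm, so that slope cancels in the within-C comparison. Placebo from A, B and D does not share it. The regimen slope variance therefore decides how far the estimate leans on borrowed controls and how large its standard error should be.

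Four regimens give three degrees of freedom for that variance, and REML often returns zero. The model then pools all placebo as if regimens were identical and reports the smallest possible standard error. Wald limits carry no allowance for this.

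At stake is a supportive claim. SAP 6.5.5 reads a significant slope difference in the favourable direction as evidence of slower progression, and limits that are too narrow would overstate that evidence.

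**Working it through.** **Inputs from the documents.** 120 active and 40 placebo in Regimen C (Protocol, RSA summary; the 3:3:2 ratio in SAP 2.6 gives 60/60/40 of 160); four regimens in the FAS; REML; multiplier 1.96.

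**Assumptions not in the documents.** 40 shared placebo in each of A, B and D (range 20 to 80), complete data, no covariates. The regimen-slope SD, τ, is varied. Its unit is the SD of a participant's estimated slope.

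**Standard error if τ were known.** Each placebo mean slope has sampling variance s² = 1/40. Let λ = τ²/(τ² + s²). The placebo reference for Regimen C is λ × (C's own placebo mean) + (1 − λ) × (mean of the four placebo groups), and

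Var(contrast) = 1/120 + (1/40) × [λ + (1 − λ)/4].

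- τ = 0: λ = 0, SE = √(1/120 + 1/160) = 0.121 (full pooling).
- τ = 0.10: λ = 0.010/0.035 = 0.286, SE = √(0.00833 + 0.025 × 0.464) = 0.141.
- τ = 0.20: λ = 0.040/0.065 = 0.615, SE = √(0.00833 + 0.025 × 0.712) = 0.162.
- τ very large: λ → 1, SE = √(1/120 + 1/40) = 0.183 (within Regimen C only).

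The contrast thus never carries the whole regimen variance.

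**Coverage with τ estimated by REML.** Ranges over repeated simulations of 20,000 to 40,000 trials per value:

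| τ | Wald coverage | REML variance = 0 |
|---|---|---|
| 0 | 94.8-95.1% | 61% of trials |
| 0.05 | 94.0-94.4% | 56% |
| 0.10 | 91.8-92.4% | 46-47% |
| 0.20 | 90.3-90.7% | 23-24% |

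The plan's nominal 95% is reproduced at τ = 0. Beyond 0.20, coverage recovers (91.2% at 0.30, 92.8% at 0.50, 94.4% at 1.0) as the estimate moves to the within-C comparison.

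**Full model.** With the unstructured 2×2 regimen covariance (2,500 trials per setting, Monte Carlo SE about 0.5 points), coverage is 94.5% at τ = 0, 91.9-92.1% at 0.10, 89.8-91.4% at 0.20 and 90.0% at 0.30. This run assumes ALSFRS-R every four weeks, participant intercept SD 6, slope SD 0.8 points/month, correlation 0.2 and residual SD 1.8. Here τ = 0.10 is 0.088 points/month.

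**Cause.** At τ = 0.20 the mean SE is 0.150 against an empirical SD of 0.171. Among trials with a zero variance estimate, Wald coverage is 89.8% at τ = 0.10 and 83.5% at 0.20.

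**Sensitivity, τ 0.10-0.30.** About 92-93% with 20 shared placebo per regimen, 89.5-91.3% with 80, and 90.8-92.4% with the three ECM regimens.

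**Does the software default help?** Hardly. ALSFRS-R is taken at seven visits from baseline to Week 24. With 120 + 4 × 40 = 280 participants, that is 1,960 observations. Subtracting two random effects each (560) leaves about 1,400 residual degrees of freedom. No random effect contains treatment × month, so the default containment method should fall back to roughly this, and t and z limits then agree.

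**Satterthwaite degrees of freedom** (one-variance version). Coverage is 95.8% at τ = 0, 95.4% at 0.05, 93.2-93.5% at 0.10 and 92.5-92.7% at 0.20. Share of excess error removed: at 0.10, (93.2 − 91.8)/(95 − 91.8) = 44%; at 0.20, (92.5 − 90.6)/(95 − 90.6) = 43%. Across checks the share runs from about a fifth to a half. Mean width rises 8-11%.

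**Kenward-Roger** (one-variance approximation, not the SAS routine). Coverage is 96.6%, 95.8%, 94.5% and 94.4% at τ = 0, 0.05, 0.10 and 0.20, with intervals roughly 30% wider. At τ = 0 the mean Wald half-width is 1.96 × 0.1304 = 0.256. Widened by 31% it is 0.335, against 1.96 × 0.1826 = 0.358 for Regimen C alone. That gives up (0.335 − 0.256)/(0.358 − 0.256) = 77% of the gain from sharing. In 39% of such trials the interval is wider than the regimen-only one.

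**The case against.** The strongest reply is that the documents point to small regimen differences. Participants are assigned to regimens at random, stratified by riluzole and edaravone use (SAP 2.5); only concurrently enrolling regimens share controls (SAP 6.1); Protocol 9.3 expects no systematic difference. Near zero, Wald coverage is 94-95%. This stands, and it makes the shortfall conditional. It does not dispose of the point: the SAP itself allows regimen slopes to vary, Regimen A is given by a different route, and SAP 6.5.13 plans to compare controls across regimens.

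The model is also only supportive. The primary analysis is Bayesian, and no test in the secondary hierarchy (SAP 6.5.1) uses this model. That stands too.

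The Master SAP, which was not available, might name a degrees-of-freedom method. But this SAP prevails over it where they differ, and the code printed here names none. The convergence fallback in SAP 6.5.12 does not answer the point: it acts only when a model fails to converge, not when it converges with a zero variance.

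A reader might infer that chance subgroup differences will look real. This is not shown. In smaller groups sampling error dominates: at τ = 0.10, Wald coverage is about 93.2% at half the sample size and 94.2-94.3% at one-fifth. Regimen slopes common to two subgroups also tend to cancel when the subgroups are compared.

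**Conclusion.** The point holds as a minor, conditional one. With four regimens and Wald limits, the FAS slope interval covers about 95% if regimens do not differ, about 94% at a regimen-slope SD of 0.05 participant slope SDs, and about 90-92% at 0.10-0.20. This rests on 120 active and 40 placebo per regimen and on regimen SDs that the documents do not give.

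Two stronger readings are tempting and unsupported. One is that the contrast carries the full between-regimen variance; C's own placebo prevents that, and coverage returns towards 95% when regimens differ greatly. The other is that 90-92% is the coverage to expect in this trial; nothing in the documents fixes the regimen SD at those values.

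The primary conclusion and the secondary testing sequence are not affected. The Satterthwaite and Kenward-Roger figures come from a one-variance model, not from SAS with the 2×2 matrix, and should be read as approximate.

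**What to change.** In SAP 6.5.5:

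1. Add ddfm=satterthwaite to the MODEL statement and replace the Wald bounds by t-based bounds.
2. Report the fitted regimen variance with each estimate.
3. Show the ERO estimate and interval beside the shared-control estimate, above all when the fitted regimen variance is zero. Satterthwaite degrees of freedom make no allowance for that case, whereas the ERO comparison does not depend on borrowed controls. ERO is already a planned analysis set.

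The cost is one SAS option, one or two sentences and one more line per table; no new data. Intervals widen by about 8-11% on average for regimen SDs of 0-0.20, with slight over-coverage (about 95.8%) if regimens do not differ. Sharing keeps most of its value: at no regimen difference, a half-width of 0.256 × 1.11 = 0.284 compares with 0.358 for Regimen C alone.

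Kenward-Roger comes closer to 95%, but at roughly 30% wider intervals it is a trade-off and not a free option. Whichever method is chosen should be fixed before unblinding.

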6.5.6 Time to Clinical Events

Time to hospitalizations and clinical events will be analyzed in the FAS, ECM, ERO, and EPP analysis sets. The summaries and analyses will parallel the analyses described for survival described in Section 6.5.4. Analysis of time to King's stage 4a or 4b and time to a 6-point decline in ALSFRS-R total score will accommodate interval censoring between ALSFRS-R assessments. Analysis of time to King's stage 4a or 4b will be stratified by baseline King's stage.

6.5.7 Composite of ALSFRS-R, SVC, and ALSAQ-40 Slopes

Participant-specific rates of change in ALSFRS-R total score, SVC percent-predicted, and ALSAQ-40 total score will be estimated in separate, endpoint-specific unadjusted random-slopes linear mixed models in the FAS, ECM, and ERO analysis sets. Participant-specific random slopes for each endpoint will be standardized to a mean of zero (0) and a variance of one (1) and then averaged for each participant. The composite average of standardized random slope estimates will be compared across treatment groups by one-way analysis of variance with adjustment for the following median-centered covariates: years since ALS symptom onset, delta-FRS, baseline riluzole use, and baseline edaravone use. A separate analysis will include baseline serum NfL level as an additional covariate. Treatment comparison between all active arm participants (i.e., the average of both 30 mg/d and 60 mg/d dosage groups) vs. placebo participants and between each active treatment group separate vs. placebo will be estimated using contrasts of least-square means.

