4.2 Exploratory Endpoints

The following categories of exploratory endpoints will be evaluated:

- Change in ALSFRS-R domain scores,
- Change in strength: hand-held dynamometry (HHD) global percentage, HHD upper extremity percentage, HHD lower extremity percentages, HHD₀, and HHD₀²,

- Change in quantitative voice characteristics as measured by Aural Analytics: maximum phonation time, pause rate, breathy vocal quality, pitch instability, regulation of voicing, articulatory precision, speaking rate, articulation rate, and monotonicity,
- Change in biofluid biomarkers of neurodegeneration and neuromuscular degeneration: serum creatinine, serum and cerebrospinal fluid (CSF) neurofilament light chain (NfL), and urinary neurotrophin receptor p75 protein extracellular domain (p75[ECD]) normalized to urinary creatinine,
- Change in patient-reported outcomes: ALSAQ-40 physical mobility, independence in activities of daily living, eating and drinking, communications, and emotional reactions domain scores and ALSAQ-40 symptom index, CNS-BFS total score,
- Change in plasma and whole blood concentrations of CNM-Au8,
- Change in CNM-Au8 PD biomarkers,
- Change in respiratory function as assessed by home spirometry,
- Time to clinical events:
 - First hospitalization due to a serious adverse event (SAE),
 - First hospitalization due to an ALS-related SAE,
 - First use of assisted ventilation,
 - First placement of a feeding tube,
 - First time reaching King's stage 4a or 4b,
 - First instance of any of the following events: feeding tube placement, tracheostomy, initiation of permanent assisted ventilation (PAV), or death,
 - First instance of any of the following events: hospitalization for an SAE, feeding tube placement, tracheostomy, initiation of PAV, or death.
- Time to first occurrence of a ≥ 6 -point decline in ALSFRS-R total score
- A composite of the standardized slope estimates for rate of change in ALSFRS-R total score, SVC percent-predicted, and ALSAQ-40 total score.

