5.7 ALSAQ-40

The description of the ALSAQ-40 instrument and item-level scores are the same as described in the M-SAP. Each of the five domains will be scored as the mean of all domain-specific items multiplied by 25 (range 0 to 100). An overall symptom index (SI) will be scored as the mean of the five domain scores. A domain score will be missing if more than 20% of the items are missing; otherwise, item non-response will be mean-imputed from other completed items from the same assessment. The ALSAQ-40 SI will be missing if any domain scores are missing. Higher scores indicate worse quality of life.

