6.5 Secondary Efficacy Analyses

6.5.1 Hierarchical Testing

Primary inference for secondary efficacy endpoints will be based on analysis of the FAS analysis set using a joint-rank comparison for the combined assessment of function and survival (CAFS (Section 6.5.2 below), a repeated-measures linear mixed model for SVC (see Section 6.5.3 below), and Kaplan-Meier product-limit estimates and log-rank test for the primary survival endpoint (see Section 6.5.4 below) with a comparison between all active arm participants (i.e., the average of both 30 mg/d and 60 mg/d dosage groups) vs. placebo participants. The sequence for testing secondary efficacy endpoints is the following:

1. CAFS,
2. SVC,
3. Survival.

If the primary analysis indicates a significant slowing in disease progression from the Bayesian shared-parameter, repeated-measures model of ALSFRS-R and mortality, then each secondary efficacy endpoint in succession would be declared significant in the specified sequence using a comparison-wise criterion of two-tailed $p < 0.05$. After the first failure to declare significance, no endpoints lower in the hierarchy can be significant. This sequential closed-testing procedure controls the overall type 1 error rate at 5%. Nominal comparison-wise p-values for secondary efficacy endpoints will also be reported.

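### The exploratory slope composite (SAP 6.5.7) averages ALSFRS-R, SVC and ALSAQ-40 without reversing ALSAQ-40, so an ALSAQ-40 benefit pulls the score the wrong way

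*SAP*

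**What the plan says.** SAP 4.2 lists the endpoint among the exploratory ones: "A composite of the standardized slope estimates for rate of change in ALSFRS-R total score, SVC percent-predicted, and ALSAQ-40 total score". SAP 6.5.7 gives the rule. A separate unadjusted random-slopes model is fitted to each endpoint in the FAS, ECM and ERO sets, and then "Participant-specific random slopes for each endpoint will be standardized to a mean of zero (0) and a variance of one (1) and then averaged". The average is compared between arms with covariate adjustment, for both doses combined and for each dose against placebo. A further analysis adds baseline NfL.

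The direction of each scale has to be taken from other sections:

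- ALSAQ-40 (SAP 5.7): "Higher scores indicate worse quality of life". The scoring there contains no inversion.
- ALSFRS-R (SAP 5.1): pre-baseline progression is the shortfall from 48, so higher is better.
- ALSFRS-R and SVC (SAP 6.5.12): high values of both define the mild end of the disease, "Early disease state (all ALSFRS-R questions scored 2 or greater, SVC 80%-predicted or greater".

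For endpoints analyzed one at a time, SAP 6.5.5 does state how to read the sign: "A significant difference in slopes in the direction of improved function would support inference". Section 6.5.7 has no such sentence.

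**The concern.** The rule gives the same positive weight to two scales on which a rise is good and one on which a rise is bad. A drug that slows decline on all three would raise the ALSFRS-R and SVC slopes and lower the ALSAQ-40 slope, so the third component subtracts from the first two.

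Once the slopes are averaged, no choice of reading repairs this. If a higher composite is taken as better, ALSAQ-40 counts backwards. If a lower one is taken as better, ALSFRS-R and SVC count backwards. The composite loses sensitivity when the three measures agree, and it can favour the drug when patients report getting worse. The same rule applies in all three analysis sets and to every dose contrast.

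**Working it through.** The plan gives no effect size or power for this composite, so there is no figure to reproduce. The algebra needs only the rule and the scale directions. The illustration needs assumptions.

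**Algebra.** Let d1, d2 and d3 be the benefits on ALSFRS-R, SVC and ALSAQ-40 in SD units of each slope, with positive meaning better. Let r be the common correlation of the three slopes once all are oriented so that higher is better.

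| | Mean difference | Variance |
|---|---|---|
| ALSAQ-40 reversed | (d1 + d2 + d3)/3 | (1 + 2r)/3 |
| As written | (d1 + d2 − d3)/3 | (3 − 2r)/9 |

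With d1 = d2 = d3 = d, the mean difference is d after reversal and d/3 as written. It is zero as written only when d3 = d1 + d2.

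**Assumptions, not in the documents.** d = 0.3, r = 0.4, two-sided 5% test, normal approximation. The 120 active and 40 own placebo participants are in the Protocol summary. SAP 6.1 shares placebo participants from regimens A, B and D, and I assume 120 of them, giving 160.

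**Standardized effect, equal benefit.**
- Reversed: 0.300/√0.600 = 0.300/0.775 = 0.387.
- As written: 0.100/√0.2444 = 0.100/0.494 = 0.202.

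**Power, equal benefit.**
- 160 placebo: SE = √(1/120 + 1/160) = 0.121. Reversed: Φ(0.387/0.121 − 1.96) = 89%. As written: Φ(0.202/0.121 − 1.96) = 39%.
- 40 placebo (ERO set): SE = √(1/120 + 1/40) = 0.183. Reversed 56%, as written 20%.
- A simulation that standardizes over the pooled sample agrees: 89.5% against 38.6%, and 55.8% against 19.8%.

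**Sensitivity, 160 placebo.**

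| d | r | Effect reversed | Effect as written | Power reversed | Power as written |
|---|---|---|---|---|---|
| 0.3 | 0.2 | 0.439 | 0.186 | 95% | 34% |
| 0.3 | 0.6 | 0.350 | 0.224 | 83% | 46% |
| 0.2 | 0.4 | 0.258 | 0.135 | 57% | 20% |
| 0.4 | 0.4 | 0.516 | 0.270 | 99% | 61% |

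For r from 0.2 to 0.6, the effect as written is 42% to 64% of the reversed one.

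**Unequal benefits (r = 0.4).**

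| d1 | d2 | d3 | Reversed | As written |
|---|---|---|---|---|
| 0 | 0 | 0.3 | +0.129 | −0.202 |
| 0.3 | 0.3 | 0 | +0.258 | +0.405 |
| 0.3 | 0.3 | −0.3 | +0.129 | +0.607 |
| 0.3 | 0.3 | 0.6 | +0.516 | 0 |

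In the first row, if higher is read as better, the composite as written is significant in the harmful direction in 36% of simulated trials with 160 placebo participants and 19% with 40.

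**Two side points on the ALSAQ-40 input.**
- Sections 4.2 and 6.5.7 refer to an ALSAQ-40 total score, whereas SAP 5.7 defines five domain scores and one overall measure: "An overall symptom index (SI) will be scored as the mean of the five domain scores".
- Both schedules of activities collect ALSAQ-40 only at Baseline and at Week 24 or early termination, while Protocol 6.6 also lists it at Week 16. With two assessments per participant, the random slope is identified only through the spread of actual visit times, and therefore weakly.

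**The case against.** The SAP is silent on reversal and does not rule it out. Section 6.5.7 gives no code, and the programmers may intend to align the signs. The Master SAP, which was not available, might define an ALSAQ-40 total. The endpoint is exploratory and lies outside the secondary hierarchy ("The sequence for testing secondary efficacy endpoints is the following", followed by CAFS, SVC and survival only). Its components are also analyzed separately, including "ALSAQ-40 domain scores and SI, and CNS-BFS total score) are revised from those specified in the M-SAP" in the random-slopes model, so a conflicting ALSAQ-40 result would be seen. The power figures rest on assumed effects and correlations, and they treat the weakly identified ALSAQ-40 slope like the other two.

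Much of this limits the weight of the point. The power figures are illustrations and not estimates for this trial, and the primary and secondary conclusions are safe. The silence is no defence, though. Section 6.5.7 states a complete rule that gives the wrong combination when followed, and it does not defer to the Master SAP. On such analyses SAP section 1 ranks this SAP above the Master SAP. The d/3 result needs no assumption about correlation or sample size.

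**Conclusion.** The point holds. As written, the composite gives ALSAQ-40 the wrong sign relative to the other two components, and its direction cannot be interpreted. An equal benefit keeps one third of its raw size. Under the stated assumptions that is 42% to 64% of the correct standardized effect, and power in the base case falls by more than half. The sign error itself depends only on the scale directions in the SAP and on following 6.5.7 literally. The size depends on the assumed d, r and number of shared placebo participants. The damage is confined to one exploratory endpoint, so this should be corrected but does not threaten the trial's main conclusions.

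**What to change.** Before unblinding, amend SAP 6.5.7 and 4.2 as follows:

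1. Multiply the standardized ALSAQ-40 slope by −1 before averaging.
2. State that a higher composite means slower progression.
3. Replace the ALSAQ-40 total score with the symptom index of 5.7, the only overall ALSAQ-40 score this SAP defines. If another total is meant, define it in the text.

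Separately, reconcile the Week 16 ALSAQ-40 listing in Protocol 6.6 with both schedules of activities.

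The cost is a few lines of SAP text and one sign in the program, with no new data. A sign change made after unblinding would look post hoc.
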